Use of maribavir in patients with ESRD including peritoneal dialysis or hemodialysis is considered as missing information in the European Union (EU) Risk Management Plan (RMP) (Takeda 2022, EU Risk Management Plan (RMP) for Livtencity (Maribavir) V0.7). To gain knowledge on the safety outcomes of this missing information, a retrospective chart review is proposed as an additional pharmacovigilance activity (EU RMP category 3).

This observational study is designed to assess the safety of maribavir for the treatment of refractory CMV infections in HSCT and SOT recipients among patients with ESRD, including patients with severe chronic renal disease requiring peritoneal dialysis or hemodialysis, in

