To date, evidence of maribavir safety is lacking in patients with post-transplant refractory CMV infection and either an eGFR <15 mL/min or an eGFR <30 mL/min receiving peritoneal dialysis or hemodialysis, and this is considered missing information in the European Union (EU) Risk Management Plan (RMP) (Takeda 2022, EU Risk Management Plan (RMP) for Livtencity (Maribavir) V0.7).

This observational (noninterventional) study is designed to assess the safety of maribavir for the treatment of refractory CMV infections in HSCT and SOT recipients among patients with ESRD and patients with severe chronic renal disease requiring peritoneal dialysis or hemodialysis in real-life conditions in the post-commercialization phase, as reported by the treating physicians. This study will also evaluate the occurrence of adverse events of special interest (AESIs), which have been recorded in the SHP620-303 trial protocol (Avery et al. 2022).

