## Figure 1Study Design Schematic

# 6.2 Setting

## 6.2.1 Study Population

This study aims to include approximately 10 adults treated with maribavir for a refractory CMV infection and who have comorbid ESRD or severe chronic renal disease requiring peritoneal dialysis or hemodialysis. The current study involves a review of routine clinical information available in the medical charts of eligible patients before the study start.

To ensure representation of several European regions, and based on maribavir launch and market uptake, the proposed study countries may include Austria, Belgium, Denmark, Estonia, France, Germany, Italy, Spain, and United Kingdom.

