# 6.2.2 Inclusion Criteria

Eligible patients must have the following attributes documented in the medical record at the time of enrolment to be included in the study:

- Adults  $\geq 18$  years of age at index date
- Diagnosis of ESRD or severe chronic renal disease prior to the index date
  - If ESRD: patient diagnosed with ESRD confirmed by an eGFR <15 mL/min
  - If severe chronic renal disease: patient diagnosed with severe chronic renal disease requiring peritoneal dialysis or hemodialysis; patient has an eGFR of 15 to <30 mL/min at index
- Patient has undergone SOT or HSCT before index date
- Patient was diagnosed with refractory (with or without resistance) CMV during the latest post-transplant period
- Patient initiated treatment with maribavir in routine practice within the eligibility period and received at least 1 dose of maribavir
- Informed consent provided (where required by local regulations) before data collection commences

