## 6.4.3 Pre Index

#### Medical history

- Chronic kidney disease history
  - Date of diagnosis of chronic kidney disease
- ESRD characteristics
  - Date of ESRD diagnosis
  - Etiology of ESRD
  - eGFR at ESRD diagnosis
- Dialysis history
  - o Type
    - Peritoneal
    - Hemodialysis
  - Start/end dates of dialysis
- CMV infection history
  - Date of onset of infection/diagnosis
  - Refractory characteristics
    - Antiviral agent to which CMV infection is refractory
    - Type of drug-resistant mutations (if applicable)
  - Classification of CMV infection
    - Asymptomatic
    - Tissue-invasive CMV disease
    - CMV syndrome
  - Prior anti-CMV prophylaxis and treatment
    - Description of prophylaxis/treatment
    - Start/end dates
    - AEs including renal toxicity from prior anti-CMV treatment
- Transplant history
  - Number of transplants prior to the current transplant
  - Date of transplant(s)
  - Type of transplant(s)
    - HSCT
      - Autologous

Takeda TAK-620-4007 Protocol Maribavir

02 June 2023

- Allogeneic
- SOT
  - Heart transplant
  - Lung transplant
  - Liver transplant
  - Pancreas transplant
  - Intestine transplant
  - Kidney transplant
  - Other transplant
- Reason for transplant(s) (underlying disease)
  - Leukemia (acute myeloid)
  - Leukemia (chronic myeloid)
  - Leukemia (acute lymphocytic)
  - Lymphoma (non-Hodgkin's)
  - Myelodysplastic syndrome
  - Other myeloid malignancy
  - Other
- Stem cell source (for HSCT)
  - Bone marrow
  - Peripheral blood stem cell
  - Cord blood
  - Other
- o CMV serostatus of donor and recipient at each transplant
  - Donor positive/recipient positive
  - Donor negative/recipient positive
  - Donor positive/recipient negative
  - Donor negative/recipient negative

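### Read literally, the two renal branches in section 6.2.2 leave out some dialysis patients whom section 4, the abstract or section 6.2.1 places in the target population

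*Protocol*

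**What the plan says.** Section 6.2.2 opens with a documentation rule: "Eligible patients must have the following attributes documented in the medical record at the time of enrolment to be included in the study". The renal criterion is "Diagnosis of ESRD or severe chronic renal disease prior to the index date", split into two branches.

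- ESRD branch: "If ESRD: patient diagnosed with ESRD confirmed by an eGFR <15 mL/min". This eGFR carries no date, and dialysis is not required.
- Dialysis branch: "patient diagnosed with severe chronic renal disease requiring peritoneal dialysis or hemodialysis; patient has an eGFR of 15 to <30 mL/min at index". This eGFR is tied to the index date and has a lower bound of 15.

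Other parts of the protocol describe the population differently.

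- Section 4 states the evidence gap as "either an eGFR <15 mL/min or an eGFR <30 mL/min receiving peritoneal dialysis or hemodialysis". It has no lower bound for dialysis patients and asks for no ESRD label.
- The abstract (Rationale and Background) says: "Use of maribavir in patients with ESRD including peritoneal dialysis or hemodialysis is considered as missing information". It gives no eGFR limit, and neither does the abstract's Population paragraph.
- Section 6.2.1 describes adults "who have comorbid ESRD or severe chronic renal disease requiring peritoneal dialysis or hemodialysis", again with no eGFR limit.

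On data, section 6.4.3 collects "eGFR at ESRD diagnosis" before index, and section 6.4.4 collects eGFR, kidney disease stage and dialysis type and start date at index. Section 6.4 makes all variables depend on what the charts hold, and section 6.8.1 says that information absent from the record is not queried.

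**The concern.** The study exists to fill a gap on ESRD and dialysis in the risk management plan, and dialysis is named in its title, research question and primary objective. An eligibility rule that a site follows exactly should not turn away patients whom the rationale counts as the gap. Under 6.2.2, whether some dialysis patients enter depends on which diagnostic label the chart uses and on whether an eGFR was recorded at index. The result can be perverse: of two dialysis patients both charted as severe chronic renal disease, one with an eGFR of 20 enters and one with an eGFR of 10 does not. Section 6.5 calls the population ultra-rare, and section 6.9 wants every available eligible patient. No analysis can recover patients who were never abstracted.

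**Working it through.** **Eligibility logic.** Take a patient on dialysis and vary three facts: whether ESRD is charted, whether an earlier eGFR below 15 is charted, and the index eGFR (none, 10, 20 or 35 mL/min as examples). Apply both branches literally. The last column applies section 4 to the index value only. The table assumes that a patient with charted ESRD can also satisfy the dialysis branch.

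| ESRD charted | Earlier eGFR <15 charted | Index eGFR | ESRD branch | Dialysis branch | Section 4 |
|---|---|---|---|---|---|
| no | yes or no | 10 | fails | fails | included |
| no | yes or no | none | fails | fails | cannot be judged |
| no | yes or no | 20 | fails | passes | included |
| no | yes or no | 35 | fails | fails | outside the cap |
| yes | no | none | fails | fails | cannot be judged |
| yes | no | 10 | passes | fails | included |
| yes | no | 20 | fails | passes | included |
| yes | no | 35 | fails | fails | outside the cap |
| yes | yes | none | passes | fails | cannot be judged |
| yes | yes | 10 | passes | fails | included |
| yes | yes | 20 | passes | passes | included |
| yes | yes | 35 | passes | fails | outside the cap |

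Row 1 contradicts section 4 directly. Rows 2 and 5 are the missing-value gap: section 4 cannot be applied to an absent index value, but the abstract and section 6.2.1 include these patients because they set no eGFR condition. Rows 9 and 12 show that an earlier confirmed value admits an ESRD patient whatever the index value.

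**Precision.** The inputs are the target of about 10 and Table 3, both in section 6.5. The exact (Clopper-Pearson) limits for x events in N patients are:

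- lower = 2.5% quantile of Beta(x, N − x + 1)
- upper = 97.5% quantile of Beta(x + 1, N − x)

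With x = 0.5N:

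- N=10, x=5: 18.7% to 81.3%, width 62.6 points. This reproduces the Table 3 entry; the other 13 cells also agree.
- N=9, x=4.5: 17.3% to 82.7%, width 65.4. Non-integer x follows Table 3, where 5% of 10 gives x=0.5.
- N=8, x=4: 15.7% to 84.3%, width 68.6.

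One patient in 10 is 10% of the target cohort. Losing one or two without replacement widens the interval by 65.4 − 62.6 = 2.8 or 68.6 − 62.6 = 6.0 points. The losses of one and two are illustrations; the documents give no count.

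**The case against.** The strongest reply is that the eGFR bands agree. Section 4's set (below 15, or below 30 on dialysis) is the same as below 15 plus 15 to <30 on dialysis, and those are the two bands in 6.2.2. On this view the bound of 15 only keeps the branches apart, and a chronic dialysis patient below 15 is an ESRD patient in all but name. The arithmetic of the bands is right, and many sites may read the criterion that way. But 6.2.2 asks for an ESRD diagnosis that the eGFR confirms. It does not say that the eGFR replaces the diagnosis, so the label gap remains for a site that follows the text. The missing-value gap is untouched by this reply.

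A second reply is that inclusion continues until the target is met (section 6.1) and that sites or countries may be added (section 6.9), so an excluded patient need not shrink the final cohort. This stands in part: the first effect is on feasibility, and precision suffers only if the patient is not replaced.

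A reader might infer more than the documents support:

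- That every dialysis patient with a missing index eGFR, or one of 30 or more, is shut out. The ESRD branch sets no date, so an earlier confirmed value below 15 admits them.
- That a recorded index eGFR of 30 or more marks a wrongly excluded patient. Section 4 itself caps dialysis patients at below 30; only the unbounded descriptions include them.
- That dialysis makes eGFR unreliable or unreported. The protocol does not say so, and neither gap depends on it.
- That the cohort will tilt toward non-dialysed ESRD, or lose a stated share of dialysis patients. The ESRD branch also admits dialysed patients, and no share can be derived.

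**Conclusion.** The point holds in a narrow form. Section 6.2.2, read literally, excludes two kinds of dialysis patient:

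1. eGFR below 15 without a charted ESRD diagnosis, in conflict with section 4;
2. no charted index eGFR and no ESRD diagnosis confirmed by an earlier value below 15, in conflict with the abstract and section 6.2.1.

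This rests on sites applying the criterion as written, including the documentation rule. How many patients it affects is unknown. It merits correction because the target is only about 10 and the remedy is small.

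**What to change.** Reconcile 6.2.2 with sections 4 and 6.2.1 in two steps.

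- Drop the lower bound of 15 from the dialysis branch, so that it covers chronic renal disease on peritoneal dialysis or hemodialysis with an eGFR below 30 at index, whether or not the chart says ESRD. This keeps section 4's upper cap.
- State that, when no index eGFR is charted, documented dialysis for chronic renal disease at index is enough for inclusion, together with the last available earlier eGFR, if any. Report eGFR descriptively, with missing values shown as missing.

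Leave the ESRD branch as it is, so that an earlier confirmed value below 15 continues to qualify.

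The cost is a wording change to one inclusion criterion before abstraction starts, carried into the eCRF eligibility check. Sections 6.4.3 and 6.4.4 already collect what is needed. The downside is slightly more heterogeneity in recorded eGFR.

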## 6.2.3 Exclusion Criteria

There are no exclusion criteria for this study

## 6.3 Data Sources

The primary source for this retrospective study will be the electronic and/or paper medical records of eligible patients included in the study. Site personnel will collect patient data from the records and enter them in a web-based electronic case report form (eCRF) hosted on an electronic data capture (EDC) platform. The eCRF will be accessible via a standard web browser. Study variables to be collected are summarized in Section 6.3.

## 6.4 Variables

All data collected in the study will be transferred into variables. Completeness of all variables may be dependent on country-specific data privacy regulations (eg, ethnicity/race). Detailed definitions of additional variables that may be derived from the collected data for the statistical analysis will be included in a separate statistical analysis plan (SAP).

The following variables will be collected at the pre-index, index, and post index periods subject to availability in the medical charts. The exposure variables capture the maribavir treatment regimen and the outcome variables capture all safety data. All other variables from this study will be presented by time period.

Current CMV infection and current transplant refer to the latest CMV infection and transplant for which the maribavir treatment was initiated.

## 6.4.1 Exposure

Maribavir treatment regimen will be captured at index and during the post index period.

Maribavir treatment initiation (at index)

- Start date of treatment
- Daily dose at treatment initiation

Changes in maribavir treatment regimen (post index)

- Changes in the treatment regimen
  - Date of change
  - New daily dose
  - Reason for changes
- Treatment completion or discontinuation
  - Date of completion
  - Date of discontinuation
  - Reason of discontinuation
    - AE/serious AE
    - Lack of efficacy
    - Patient decision
    - Physician decision
    - Death
    - Other

# 6.4.2 Variables to Address Study Outcomes

Safety data will be collected during the index and post index period, including days after the completion of maribavir treatment or treatment discontinuation. The primary outcome is the incidence of AEs. The secondary outcome is the incidence of AESIs.

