# AEs

- AE description
  - o AESI
    - Immunosuppressant drug concentration level increased
    - Tissue-invasive CMV disease
    - Relapse or progression of the underlying disease for which the transplant was performed
    - Taste disturbance (dysgeusia)
    - Nausea
    - Vomiting
    - Diarrhea
    - Invasive fungal or bacterial infections
    - GVHD
- Start/end dates
- Serious AE/nonserious AE
- AE severity
  - o Mild

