#### 02 June 2023

- Current CMV infection
  - Date of onset of infection/diagnosis
  - Refractory characteristics
    - Antiviral agent to which CMV infection is refractory
    - Type of drug-resistant mutations (if applicable)
  - Agent that patient is refractory to
  - o Classification of CMV infection
    - Asymptomatic
    - Tissue-invasive CMV disease
    - CMV syndrome
  - Prior anti-CMV medication used to treat the current CMV infection
    - Induction and maintenance therapy received for transplant, rejection treatment, and other adjuvant/related therapy
    - Start/end dates
    - Other anti-CMV prophylaxis and treatment
    - Other anti-infective agents
  - AEs including renal toxicity from prior anti-CMV treatment
- Current transplant status
  - Date of transplant
  - Type of transplant
    - HSCT
      - Autologous
      - Allogeneic
    - SOT
      - Heart transplant
      - Lung transplant
      - Liver transplant
      - Pancreas transplant
      - Intestine transplant
      - Kidney transplant
      - Other transplant
  - Reason for transplant
    - Leukemia (acute myeloid)
    - Leukemia (chronic myeloid)
    - Leukemia (acute lymphocytic)
    - Lymphoma (non-Hodgkin's)
    - Myelodysplastic syndrome
    - Other myeloid malignancy
    - Other
  - Stem cell source (for HSCT)
    - Bone marrow
    - Peripheral blood stem cell
    - Cord blood
    - Other

02 June 2023

- o CMV serostatus
  - Donor positive/recipient positive
  - Donor negative/recipient positive
  - Donor positive/recipient negative
  - Donor negative/recipient negative
- Current GVHD status (for HSCT patients only)
  - Acute GVHD status
    - Presence
    - Absence
    - Grade
  - Chronic GVHD status
    - Presence
    - Absence
    - Grade
- Relevant comorbidities ongoing or diagnosed at index date and treatment

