# 6.7.1 Statistical Methods

Unless otherwise specified, all statistical analyses will be descriptive in nature. Continuous variables will be described by the number of eligible participants and missing data, mean, standard deviation, median, first quartile, third quartile, and minimum and maximum values. Categorical variables will be described as the total number of participants and relative percentage per category. Percentages will be calculated using the most appropriate denominator. Two-sided 95% CIs will be reported as appropriate.

Should missing data occur, missing data will not be imputed and the data will be analyzed as they are recorded in the study eCRFs. However, for all missing dates, some date imputation may be performed. The general imputation rules will be described in the SAP. Missing data may be included as a separate category in some cases, depending on the nature of the variable. Unless otherwise specified in a table's footnote, missing values will not be included in the denominator for summarizing a categorical variable's distribution. If the eCRF includes a selection of "unknown," these responses will not be considered missing responses and will be included in the distributions.

Descriptive analysis will be performed on the variables listed in Section 6.4. Year of birth will be analyzed as age and age group, and dates would be as duration or index days/weeks. Detailed definitions of additional variables that may be derived from the collected data for the statistical analysis will be included in a separate SAP.

Incidence of each outcome will be expressed per person-year of exposure to account for varying length of follow-up. Incidence rates will be calculated as the number of patients with an event of interest, divided by the number of person-years at risk, ie, the summed person-year of maribavir exposure. Only new cases will be included in the numerator; patients with existing AEs at the index date who reported the AE before the index date will not be counted, and patients who initially experience AEs at index or at the post index date will be counted only once in the numerator (ie, worsening outcomes will not be counted as new cases). The following definitions will be used to estimate incidence rates:

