# SAEs, AEs, special situation report, and product quality complaints in the medical chart records or other applicable source data that are not part of the study objectives and endpoints

Events/complaints that are not part of the study objectives and endpoints will not be abstracted or collected from medical chart records or other applicable source records.

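### The new-cases-only rule in 6.7.1 needs any-cause status at index, which the variable list omits for most AESIs, and it drops prevalent patients from the numerator but not from the person-time

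*Protocol*

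**What the plan says.** **The rule.** Section 6.7.1 restricts the incidence-rate numerator to new cases: "patients with existing AEs at the index date who reported the AE before the index date will not be counted". It adds that "worsening outcomes will not be counted as new cases". The denominator is the person-years at risk, which the section equates with summed maribavir exposure. Each patient's person-days end at the outcome, 7 days after the last dose, death or the end of data.

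**Data from index onward.** Section 6.4.2 says "Safety data will be collected during the index and post index period". Each recorded event carries "Start/end dates", whatever its cause.

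**Data before and at index.** The only item labelled as an adverse event is "AEs including renal toxicity from prior anti-CMV treatment", listed in 6.4.3 and again under the current CMV infection in 6.4.4. Section 6.4.4 also lists GVHD status (HSCT patients only), the CMV classification (which includes tissue-invasive disease), concomitant medications and "Relevant comorbidities ongoing or diagnosed at index date and treatment". The word relevant is not defined.

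**Limits on abstraction.** Section 8.2 says "Events/complaints that are not part of the study objectives and endpoints will not be abstracted or collected from medical chart records". Section 6.8.1 says that information absent from the chart is not queried.

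**The concern.** A first-event rate requires a set of patients free of the event at the start. Here that set depends on what was present at index from any cause, but the variable list asks about earlier adverse events only when they came from a prior antiviral. Chronic gastrointestinal symptoms or taste disturbance from another source have no field of their own. Section 4 names diarrhea, dysgeusia, nausea and vomiting among the events most commonly seen with maribavir, so the gap falls on events of particular interest.

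The study has one cohort and no comparator (Appendix B), so a carried-over symptom counted as new is not offset by the same error in another arm. The SAP cannot supply the missing status: section 6.4 leaves to it variables derived from collected data, and a status that was never abstracted cannot be derived.

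**Working it through.** **Step 1: which AESIs have a listed status at index.** From 6.4.2 to 6.4.4:

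| AESI | Any-cause index status listed? |
|---|---|
| GVHD | Yes, HSCT patients only |
| Tissue-invasive CMV disease | Yes, through the CMV classification |
| Nausea, vomiting, diarrhea, dysgeusia | No |
| Invasive fungal or bacterial infection | No |
| Raised immunosuppressant level | No |
| Relapse or progression of underlying disease | Reason for transplant only, no disease status |

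Two of nine have a dedicated status. The point rests on the six events in rows three to five.

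**Step 2: what the other data recover.** A charted onset before index gives a start date before index, and the rule then works. An infection under treatment may show in comorbidities or concomitant medications. Two gaps remain: a symptom whose onset is not charted and that is not judged a relevant comorbidity, and a patient with no entry, who may have been symptom-free or simply not documented.

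**Step 3: numerator and denominator.** The rule says prevalent patients are not counted. Nothing in 6.7.1 takes their exposure out of the person-time, although they cannot have a first event.

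**Step 4: illustration.** The protocol gives no figure for this point. Table 3 concerns proportions; its exact intervals reproduce (for example 2.5% to 55.6% at 20% of 10), but they do not describe this error. Inputs:

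- 10 patients (6.5).
- 63 days each: the 8 weeks of the Phase 3 trials (section 4) plus the 7-day grace period (6.1). This is an assumption, because treatment length here is not fixed.
- Person-time not stopped at the event, a simplification. Stopping it, as 6.7.1 does, would raise all the rates.

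Person-time is 10 × 63 / 365 = 1.73 years.

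- 2 events: 2 / 1.73 = 1.16 per person-year (exact 95% CI 0.14 to 4.19).
- 3 events: 3 / 1.73 = 1.74 per person-year (0.36 to 5.08).

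One miscounted case therefore adds 0.58 per person-year.

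Now assume that 2 of the 10 have the symptom at index and that 2 of the other 8 develop it. At-risk person-time is 8 × 63 / 365 = 1.38 years, and the first-event rate is 2 / 1.38 = 1.45. Under 6.7.1 as written:

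| Prevalent patients recognised | Events counted | Rate per person-year | Ratio to 1.45 |
|---|---|---|---|
| Both | 2 | 1.16 | 0.8 |
| One | 3 | 1.74 | 1.2 |
| Neither | 4 | 2.32 | 1.6 |

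The two defects pull in opposite directions. Missed prevalence raises the rate, and recognised prevalence left in the denominator lowers it.

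**The case against.** The strongest reply is that the start date already applies the rule. Charts are reviewed back to the diagnosis of the kidney or underlying disease, by investigators involved in care or their delegates (6.1). A symptom charted before index has a start date before index and drops out. Comorbidities and medications at index add to this, 6.9 discloses dependence on chart quality, and with about 10 patients the planned listings and narratives allow each case to be read. Much of this stands, and it confines the problem to the gaps in step 2. Those gaps remain: listings show only what was abstracted, absent information is not queried, and the protocol disagrees with itself on missing dates (6.7.1 allows some imputation, 6.9 rules it out for exposure and outcome dates).

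It can also be said that the proposed field will read *not documented* where the chart is silent. That is true. The gain is a prompt to the abstractor and a visible count of unknowns.

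On the denominator, the words at risk could be taken to exclude prevalent patients. The section's own gloss, summed maribavir exposure, does not do so.

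Three stronger readings are tempting and are not supported:

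- That the at-risk set cannot be formed at all. It can, from start dates, subject to chart gaps.
- That earlier symptoms from an antiviral are reliably removed while those from other causes are not. The prior-treatment item lists no onset date or ongoing status for the event itself, so both kinds depend mainly on the start date.
- That AESI percentages shift by 10 points per case. Section 6.7.1 states the rule for incidence rates; 6.7.1.1 and 6.7.1.2 report percentages without clearly applying it.

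**Conclusion.** The point holds in a limited form. The new-case rule calls for a status that the variable list does not collect for most AESIs, and the numerator and denominator treat prevalent patients differently. Carried-over events with a charted onset are caught; those without can enter as incident. The net direction is not fixed.

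The size cannot be computed, because the protocol gives neither the share of patients with these symptoms at index nor the share whose onset is uncharted. A reader might assume that every prevalent case is missed: with a new-onset risk of 20% and 10% to 40% prevalent at index, the counted share would be 28% to 52%. That ignores the start dates and rests on invented prevalences, so it should not be used. The figures 1.16 and 1.74 show only what one patient is worth at this sample size. Wide intervals do not cover the problem, since they express sampling error and not misclassification.

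**What to change.** - **6.4.4 (Index):** for each of the nine AESIs, record status at index from any cause as *present*, *absent* or *not documented*, with the onset date or *before index, date unknown*.
- **6.7.1:** for each AESI's first-event rate, remove patients with that AESI present at index from both the numerator and the person-time. Keep patients whose status is not documented in the main rate, and add one sensitivity analysis that excludes them.
- **6.7.1.2:** report the number with each AESI present at index beside its incidence.

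The cost is slightly more abstraction time in about 10 charts that are already opened for the pre-index history, and some undocumented entries. Appendix A lists the data management plan and the SAP as still to be developed, and 6.6 places approval of the former before the database design is final, so the field can go in before the build. The change covers the AESIs only; for other events the start date remains the means of applying the rule.
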